6.6. Duration of Study Participation

6.6.1. Treatment Discontinuation

Discontinuation from study medication does not mean discontinuation from the study, and remaining study procedures should be completed as indicated by the study protocol. If a clinically significant finding is identified (including but not limited to changes from baseline) after enrollment, the investigator or qualified designee will determine if any change in participant management is needed. Any new clinically relevant finding will be reported as an AE. The following events are considered sufficient reasons for discontinuing a subject from study medication:

- If any clinical AE, laboratory abnormality, or other medical condition or situation occurs such that continued treatment with study medication would not be in the best interest of the participant.
- If the participant meets an exclusion criterion (either newly developed or not previously recognized) that precludes further study participation. Discussion with the Medical Monitor is recommended.
- Worsening of illness which requires discontinuation of study medication at the discretion of the treating physician.
- Subject withdrawal from treatment (subject no longer wants to receive study medication but is willing to have additional data collected), which must be documented in subject's medical record. It must be confirmed in documented communications whether or not AEs are leading the subject's choice to withdraw from the study medication.
- Death
- Protocol violation; discussion with the Medical Monitor is recommended.
- Pregnancy
- Loss to follow-up
- Completion of study treatment according to the study protocol.

Reason for study treatment discontinuation must be recorded in the electronic case report form (eCRF) and source documents.

6.6.2. Study Discontinuation

The following events are considered sufficient reasons for discontinuing a subject from the study:

- Screen failure
- Subject withdrawal from study (subject no longer wants to participate in the study and is willing to have additional data collected), which must be documented in subject's medical record. It must be confirmed in documented communications whether or not AEs are leading the subject's choice to withdraw from the study.
- Significant study intervention non-compliance
- Death
- Loss to follow-up
- Protocol violation; discussion with the Medical Monitor is recommended

Reason for study discontinuation must be recorded in the eCRF and source documents.

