Subject will receive up to 3 doses of CYNK-001 on Days 1, 4, and 7. A minimum of 2 doses is required for efficacy assessment. After the first dose, subsequent infusions on Days 4 and 7 will be provided only if no toxicity of Grade 3 and above (either related or unrelated to CYNK-001) is observed.

Study Design:

The study will include a Phase I portion wherein a total of 14 subjects will be enrolled to assess the safety and efficacy of CYNK-001. To evaluate the safety for potential dose limiting toxicities (DLTs), this phase will enroll 3 subjects initially treated with CYNK-001. The safety data for these 3 subjects will be evaluated 24 hours after the final dose was provided to the 3rd subject.

If deemed safe, the remaining 11 subjects will be enrolled and monitored per the safety stopping rule until Study Day 15 where the first CYNK-001 infusion occurs on Day 1. If any DLT is observed in the first three subjects, the DMC will be convened for a recommendation. For the remaining 11 subjects, DMC will be convened if the safety stopping rule is met. Overall, in case of 2 out of the 6 subjects had experienced DLTs in the Phase I portion of this study, the DMC will be convened for safety evaluation. Subjects treated in the Phase I portion of the study will be treated in the inpatient setting.

The starting dose of 150×10^6 cells was selected as a desensitizing dose on Day 1 followed by 600×10^6 cells on Days 4 and 7. The DLTs will be evaluated through Study Day 28 following the first dose of CYNK-001 infusion (Day 1). Once CYNK-001 is deemed safe per the stopping rules and if efficacy is established in at least 2 out of the 14 subjects by Study Day 15, Phase II portion of the study will be initiated.

The Phase II portion of the study is a randomized, open-label, multi-site study. Subjects will be randomized into either CYNK-001 or Control group with best supportive care alone as defined by the institutional practice by 1:1 ratio. All subjects in both Phase I and Phase II will receive the best supportive care. Subjects treated in the Phase II portion of the study may be treated in the outpatient setting, if deemed safe based on Phase I data review and recommendation by the DMC.

The study is divided into 3 study periods:

Screening Period

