As a preliminary proof of concept study without relevant data for the new coronavirus disease, 1-sided α of 0.05 will be used in the sample size consideration. With a sample size of 36 for each group (72 in total with 1:1 randomization ratio), a reduction of 50% for the time to event efficacy of CYNK-001 comparing with control can be detected with a power of at least 81% (assuming the time to

clinical improvement is 8 days or earlier for CYNK-001 group, and 16 days or earlier for the control group with the same reduction of 50%) by using Log-rank test. This estimation is based on the study design with a maximum follow up of 28 days for each subject for primary analysis.

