6.5. Dose Adjustment Criteria

Dose adjustments may occur if clinically indicated by the treating physician. In general, the following should be followed:

- Dose reductions are not permitted in this study. If any DLTs were observed, the dose de-escalation treatment with reducing frequency of doses will be implemented per the DMC recommendation.
- Should dose delays for CYNK-001 be required:

- Day 1 will be the date of initial dose
- Day 4 dose may be delayed up to 48 hours
 - For non-safety reasons: If delayed longer than 48 hours, Day 4 dose will be skipped., and the subject will receive the Day 7 dose. If the Day 4 dose is given within 48 hours, the Day 7 dose will be delayed for three days from the actual day of when Day 4 dose was given (Ex: if Day 4 dose is given on Day 5, then Day 7 dose will be given on Day 8)
 - For safety reasons: Day 4 dose could be delayed if \geq Grade 3 toxicity is observed after the first dose. In such cases, Day 4 dose is provided only if the event is resolved or reduced to Grade 1 toxicity level. If the toxicity did not resolve within 48 hours, the Day 4 dose will be skipped. If the Day 4 dose is given within 48 hours, the Day 7 dose will be delayed for three days from the actual day of when Day 4 dose given.
 - If the subject has worsening of illness, study medication will be stopped.
- Day 7 dose may be delayed up to 48 hours:
 - For non-safety reasons: If delayed longer than 48 hours, the subject will not receive additional therapy.
 - For safety reasons: If Day 4 dose was delayed but given within 48 hours of planned Day 4, then the Day 7 dose will be delayed for three days from the actual day of when Day 4 dose was given.

If Day 4 dose was given as planned, Day 7 dose could be delayed if \geq Grade 3 toxicity is observed after the second dose. If Day 4 dose was skipped, Day 7 dose could be delayed if \geq Grade 3 toxicity is still observed after the first dose. In such cases, Day 7 dose is provided only if the event is resolved or reduced to Grade 1 toxicity level. If the toxicity did not resolve within 48 hours of the scheduled day, the Day 7 dose will not be administered.
 - If the subject has worsening of illness, study medication will be stopped.
- All subjects who receive any amount of CYNK-001 will be followed to 6 months or until loss to follow-up, death, or withdrawal from study, whichever occurs first.

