14.2. Study Population Definitions

The following analysis populations are planned for this study:

- Safety Population – include all subjects who receive any amount of CYNK-001 or who enroll into the control group.
- ITT Population – include all randomized subjects.

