13.3 Analysis Methods

The primary endpoints will be analyzed with hypothesis testing procedures. No formal hypothesis will be carried out for secondary endpoints and the p-values are provided for informative purpose only.

Missing data and censoring will be handled as described below.

- **Primary Efficacy Analysis**

Phase II efficacy data will be analyzed for the ITT population based on randomized treatment group.

The primary efficacy endpoint is the time to clinical improvement on or before Day 28. Kaplan-Meier estimates of the survival curve, estimate of median survival time and its 95% CI will be calculated. Log-rank test will be used to test the difference between treatment groups while adjusting for pre-defined age strata.

Hazard ratio will be estimated via proportional hazard model using treatment as a factor stratified by age group.

Subjects who withdraw after randomization and before any measurements assessed will be censored at randomization date; subjects who terminate from the study before Day 28 without clinical improvement will be censored on the date of the last visit; and subjects who died without clinical improvement by OSCI will be censored on Day 28; subjects without clinical improvement ~~who have no event~~ on or before Day 28 will be censored on Day 28.

- **Secondary Endpoints Analyses**

The analysis will be based on the ITT population unless otherwise specified. Since the purpose of the analysis is for hypothesis generation, no multiplicity adjustment or adjustments for stratification covariates (age and site strata) will be made.

For the endpoints of event rate, including:

- Proportion of subjects who achieved clinical improvements by OSCI

- Proportion of subjects with clearance of SARS-CoV-2 by rRT-PCR
- Proportion of subjects who had pulmonary clearance by LRT specimens where it has previously been found
- Proportion of subjects who need invasive or non-invasive ventilation
- Proportion of subjects who died

The proportions and their two-side 95% CIs will be calculated. Fisher's exact test will be used to test the difference between treatment groups. If the subject has no data after baseline, the subject will be considered as failure in the analysis.

For endpoints of time to event, including:

- Time to clinical improvement measured by NEWS2 Score
- Time to clearance of SARS-CoV-2 by rRT-PCR testing
- Time to disappearance of virus from LRTI specimen
- Time from randomization to medical discharge

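### Off-study reasons in Protocol 6.6.2 conflict with 6.5 and 6.6.1 and, with last-visit censoring in SAP 13.3, could cause informative censoring in the CYNK-001 arm; the synopsis two-dose sentence also contradicts ITT

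*Protocol*

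**What the plan says.** **Stopping drug.** Protocol 6.6.1 states: "Discontinuation from study medication does not mean discontinuation from the study, and remaining study procedures should be completed". Its reasons for stopping medication include worsening of illness, protocol violation, and a subject who declines more infusions but will still give data. Section 6.5 adds: "If the subject has worsening of illness, study medication will be stopped". The same section follows everyone given any amount of CYNK-001 for six months, unless the subject is lost, dies or withdraws.

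**Leaving the study.** Protocol 6.6.2 lists "Significant study intervention non-compliance" and protocol violation as sufficient reasons to discontinue a subject from the study. It describes withdrawal from the study as the case where the "subject no longer wants to participate in the study and is willing to have additional data collected".

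**Censoring.** Protocol 6.9 censors every subject without improvement at Day 28, with no exception for leaving early, and SAP 13.1.2 repeats this. SAP 13.3 instead says that "subjects who terminate from the study before Day 28 without clinical improvement will be censored on the date of the last visit". It holds deaths without improvement, and other non-improvers, to Day 28.

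**Who is analysed.** The synopsis says: "A minimum of 2 doses is required for efficacy assessment". It names neither a phase nor an analysis set. Protocol 14.2 has the ITT population "include all randomized subjects". SAP 7 defines it the same way, and SAP 13.3 uses it for the Phase II analysis. SAP 13.1.1 analyses Phase I efficacy on the safety population, which needs only some CYNK-001 to have been given.

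**The concern.** One event can lead to two outcomes. Protocol violation is a reason to stop drug in 6.6.1 and a reason to leave the study in 6.6.2, with no rule for choosing. Willingness to give more data marks the treatment-only withdrawal in 6.6.1 and the full withdrawal in 6.6.2.

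The choice reaches the primary endpoint. A subject who is not improving counts as a non-improver through Day 28 if kept on study. Under SAP 13.3 the same subject drops out of the risk set at the last visit if taken off study.

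Exposure to the rule is unequal, because only CYNK-001 subjects have infusions to miss. In an open-label trial, the person judging whether non-compliance is significant knows the arm and how the subject is doing. If those removed are mostly doing badly, an inert product would appear to shorten time to improvement.

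No planned analysis would show this. The only sensitivity set (SAP 13.4) is per-protocol, limited to treated subjects without major deviations, and could drop the same subjects again.

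**Working it through.** **Inputs from the documents.** 36 per arm; times of 8 and 16 days; 28-day follow-up; power of at least 81%; "1-sided α of 0.05 will be used in the sample size consideration" (synopsis). SAP 4.5 sets two-sided 0.05 for reported p-values. Neither document gives a rate of removal from study, so the number removed, k, is an assumption.

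**The plan's own figure.** Read 8 and 16 days as exponential medians.

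- Improved by Day 28: 1 − 2^(−28/8) = 0.912 and 1 − 2^(−28/16) = 0.703.
- Expected events: 36 × (0.912 + 0.703) = 58.1.
- Freedman power, one-sided 0.05: Φ(√58.1 × (1 − 0.5)/(1 + 0.5) − 1.645) = Φ(2.541 − 1.645) = 0.815.

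The stated 81% is reproduced, with every subject followed to Day 28 and no dropout.

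**Why early censoring matters.** The log-rank numerator is the sum over event days of d1 − d × n1/(n1 + n0), where d1 is CYNK-001 events, d all events, and n1 and n0 the numbers at risk. Censoring a CYNK-001 non-improver lowers n1 and leaves d1 unchanged. As an illustration, going from 36 to 32 at risk against 36 controls cuts the expected CYNK-001 share of events from 36/72 = 0.500 to 32/68 = 0.471.

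**Simulation under no true effect.** Both medians are 16 days, with whole-day times, an unstratified log-rank test and 2,000 runs per cell (4,000 with no removal). With nobody removed, the one-sided rejection rate is 0.048 and the improvement rate ratio 0.99. With k CYNK-001 subjects censored at Day 4:

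| k of 36 | All non-improvers (rate ratio) | Unrelated to later outcome | Would all have improved |
|---|---|---|---|
| 2 | 0.10 (1.10) | 0.046 | 0.040 |
| 4 | 0.19 (1.21) | 0.052 | 0.022 |
| 6 | 0.30 (1.33) | 0.051 | 0.016 |
| 8 | 0.48 (1.50) | 0.052 | 0.010 |

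- Censoring four control non-improvers at Day 4 instead gives 0.014 (rate ratio 0.83).
- At the 1.96 cut-off of a two-sided test, false positives in favour of CYNK-001 go from 0.026 with no removal to 0.12 with four CYNK-001 non-improvers censored.
- For scale, 36 × (1 − 0.703) = 10.7 non-improvers are expected per arm under this null, so four is about 37% of them.

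**If the two-dose sentence were applied as an exclusion.** Excluding 2, 4, 6 or 8 CYNK-001 non-improvers gives 0.12, 0.21, 0.35 and 0.56. Excluding subjects not improved by Day 4, but otherwise without regard to outcome, gives 0.06 to 0.09.

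**The case against.** A reader might infer that a CYNK-001 subject who worsens is taken off study, so that all such subjects vanish from one arm. The documents do not say that. Worsening is a reason to stop medication in 6.5 and 6.6.1, and it is not on the 6.6.2 list. A dose skipped as 6.5 directs is compliance with the protocol. The follow-up promise in 6.5 covers everyone infused, and Section 11 has OSCI recorded daily, by phone for outpatients. Removal therefore needs a judgement of significant non-compliance, a violation or a withdrawal. This stands, and it is why the bias is only possible. The promise still yields to withdrawal from the study, and it does not cover a subject randomised to CYNK-001 and never infused.

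A reader might also take the two-dose sentence as the planned analysis set. It is not: every definition of the Phase II primary set is all randomised, and even the per-protocol set does not name a dose count. What remains is a contradiction. SAP 4.8 leaves room for misreading, because it calls the main efficacy set a full analysis set that SAP 7 never defines.

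Nor does the sentence make the Phase I gate easier to pass. The gate is a count of at least 2 improvers, and excluding subjects cannot add one.

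Finally, withdrawal and protocol violation apply to both arms, and the withdrawal bullet may simply lack the word not. Both points are fair. Only the non-compliance reason is specific to the arm with infusions.

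**Conclusion.** The conflicts are in the text and should be resolved. The off-study reasons in 6.6.2, combined with last-visit censoring, open a route to informative censoring that could fall mainly on the CYNK-001 arm. If those removed are non-improvers, it favours CYNK-001: 4 of 36 censored at Day 4 takes one-sided type I error from 0.05 to about 0.19. That figure assumes exponential times with a 16-day median, removal of non-improvers only, and no removals from control. The direction depends on who leaves and why, so the documents do not support saying that the comparison is tilted, only that it could be.

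The two-dose sentence contradicts both the ITT definition and the Phase I safety-population analysis, but ITT remains the stated Phase II analysis.

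SAP 15 records that the trial closed after 7 Phase I subjects were dosed. This is a flaw in the plan, and no Phase II result is affected.

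**What to change.** 1. In Protocol 6.6.2, remove non-compliance and protocol violation as reasons to leave the study. Add no new reason for stopping treatment to 6.6.1.
2. Correct the withdrawal bullet to subjects who are not willing to have further data collected.
3. State that every randomised subject, whatever was infused, continues OSCI and scheduled visits to Day 28 and Month 6 unless consent for data collection is withdrawn.
4. Delete the two-dose sentence from the synopsis, or limit it to a named supportive set. Define the full analysis set in SAP 4.8 or replace it with ITT.
5. Align the censoring rules in Protocol 6.9 and SAP 13.3, and add a sensitivity analysis that holds early leavers as non-improvers to Day 28.

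The cost is protocol and SAP wording, one extra analysis, and calls and visits already scheduled for other subjects. With everyone followed, the simulated one-sided error is 0.048. The 81% power is unchanged, because it already assumes no dropout. As the trial is closed, the changes matter if this plan is reused.

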6.6.3. Subject Withdrawal

Subjects may withdraw voluntarily from the study at any time upon request. Information related to the subject withdrawal must be well documented in the source document, including the documentation associated with any AEs the subject may or may not be experiencing at the time of the withdrawal.

Subjects who withdraw from the study after a single dose of CYNK-001 treatment will not be replaced.

6.7. Criteria for Study Termination

The study may be terminated for the following reasons:

- Study is completed as planned.
- The study is terminated based on lack of evidence of therapeutic benefit.

Celularity also reserves the right to terminate this study prematurely at any time for reasonable medical or administrative reasons. Any premature discontinuation will be appropriately documented according to local requirements (e.g., IRB/EC, regulatory authorities, and others as applicable).

In addition, the Investigator or Celularity has the right to discontinue a single site at any time during the study for medical or administrative reasons such as:

- Unsatisfactory enrollment
- GCP non-compliance
- Inaccurate or incomplete data collection
- Falsification of records
- Failure to adhere to the study protocol
- Number of subjects not following the study protocol plan surpasses the statistical drop-out rate assumption resulting in the study being underpowered.

6.8. End of Trial

[figure not shown]
The End of Trial is defined as either the date of the last visit of the last subject to complete the post-treatment follow-up, or the date of receipt of the last data point from the last subject that is required for primary, secondary and/or exploratory analysis, as specified in the protocol, whichever is the later date.

6.9. Efficacy Endpoint Definitions

- **Time to Clinical Improvement by OSCI**: defined as the time from the date of randomization to the first date of clinical improvement measured by OSCI. (Appendix D). Clinical improvement is defined as an improvement at least by cross category (or Patient State improvement in Appendix D table, such as from Hospitalized Severe Disease to Hospitalized Mild Disease). Subjects who do not have clinical improvement on or before Study Day 28 will be censored at Study Day 28.
- **Clinical Status by OSCI**: defined by the Ordinal Scale score of 0 to 8 by OSCI (Appendix D).
- **Rate of Clinical Improvement by OSCI**: defined as the proportion of subjects who achieved clinical improvement by OSCI.
- **Time to Clearance of SARS-CoV-2**: defined as the time from the date of randomization to the clearance of SARS-CoV-2 by rRT-PCR by two negative results at least 24 hours apart, with the first negative as the start date of clearance. Specimens included are nasopharyngeal swab and oropharyngeal swab (if available). Subjects who do not have clearance on or before Day 28 will be censored at Day 28.
- **Rate of Clearance of SARS-CoV-2**: defined as the proportion of subjects with “negative” measurement of COVID-19 by rRT-PCR.
- **Time to Clinical Improvement by NEWS2**: defined as the time from the date of randomization to the first date of clinical improvement. Clinical improvement is defined as improvement of clinical symptoms as measured by the NEWS2 Score (Appendix C). Subjects who do not have clinical improvement on or before Study Day 28 will be censored at Study Day 28.
- **Rate of Clinical Improvement by NEWS2**: defined as the proportion of subjects who achieved clinical improvement.
- **Time to Pulmonary Clearance**: defined as the time of randomization to the date of pulmonary clearance. This is defined as disappearance of virus from LRT- specimen where it has previously been found (induced sputum if available, endotracheal aspirate if available). Subjects who do not have pulmonary clearance on or before Study Day 28 will be censored at Study Day 28.
- **Pulmonary Clearance Rate**: defined as the proportion of subjects who achieve pulmonary clearance.

- **Duration of Hospitalization:** defined as date of randomization to the date of medical discharge. Subjects who are not discharged on or before Study Day 28 will be censored at Study Day 28.
- **Ventilatory Support:** For those subjects requiring ventilatory support or supplemental oxygen during the treatment period:
 - Supplemental oxygen-free days
 - Proportion of subjects developing respiratory failure requiring invasive or noninvasive mechanical ventilation.
- **SOFA Score:** For those subjects evaluated by Sequential Organ Failure Assessment (SOFA) scores from ICU admission through ICU discharge (for subjects requiring intensive care). Mean arterial pressure should be measured with an arterial line. See [Appendix A](#).
 - Organ support, according to the number of days within the 28 days starting from Day 1 when subjects do not receive specific forms of support:
 - a. Supplemental oxygen-free days
 - b. Renal replacement therapy-free days
 - c. Vasopressor-free days
 - d. Invasive or non-invasive mechanical ventilation free days
 - e. Organ support-free days (that is, days free of invasive mechanical ventilation, renal replacement therapy and vasopressors)
 - f. Extracorporeal circulation support-free days
- **Mortality Rate:** defined as the proportion of subjects who died by any cause.

Figure 2: Study Schema

[figure not shown]
